### **9.3.3 Safety Analyses**

To describe the overall safety of ancestral strain and updated (if administered) Novavax vaccine(s) administered as a second (or subsequent) booster following licensed mRNA vaccines and a first ancestral strain Novavax vaccine booster, the secondary endpoints of safety data include solicited AEs in the 7 days following study vaccination and MAAEs, AESIs (including myocarditis and/or pericarditis), and SAEs throughout the study. All safety analyses will be descriptive and conducted using the Safety Analysis Set.

All local/systemic solicited (reactogenicity) AEs within the post-vaccination window (Days 1-7) by the verbatim terms, and by severity (mild, moderate, severe) using the maximal severity observed for the specific symptom post-vaccination will be summarized for each study vaccine group.

Unsolicited MAAEs, AESIs (including myocarditis and/or pericarditis), and SAEs throughout the study will be summarized by the study vaccine group and by SOC and PT using MedDRA terms, as well as by severity and relationship to the study vaccine to present the number and percentage with its corresponding exact 95% CIs using Clopper-Pearson method. For multiple occurrences of an AE in the same participant, a participant will be counted only once within an SOC or a PT, using the most severe occurrence and closest reported relationship for the summarization by severity or relationship to the study vaccine, respectively. The duration of MAAEs, AESIs, and SAEs through Day 181 will also be summarized.

A by-participant listing of MAAEs, AESIs, and SAEs throughout the study will also be provided.

#### 9.3.3.1 Prior and Concomitant Medications and Vaccinations

Prior and concomitant medications and vaccinations will be summarized by study vaccine group and preferred drug name as coded using the WHO drug dictionary for all participants in the Safety Analysis Set. Multiple occurrences of medication usage for a participant will be counted only once within an anatomical therapeutic chemical (ATC) term and standardized medication name. A by-participant listing of prior and concomitant medications (including vaccines) will be presented.

#### 9.3.3.2 Vital Sign Measurements

Vital sign measurements including temperature, respiratory rate, blood pressure, and pulse rate will be summarized as continuous variables. A by-participant listing of vital signs will be provided.

#### 9.3.3.3 Physical Examinations

Physical examination at Screening or Day 1 will include height and weight, cervical and axillary lymph nodes, and heart, and any other areas based on participant symptoms. A targeted examination will be performed at unscheduled visits.

### 9.4 Interim Analyses

The 1st interim analysis will be performed when the complete data for Nab titers and/or IgG GMEUs and/or hACE2 titers for the ancestral strain Novavax vaccine and safety data from Day 1 through Day 29 are available.

The 2nd interim analysis will be performed when the complete data for Nab titers and/or IgG GMEUs and/or hACE2 titers for an updated Novavax vaccine are available.

The first and second interim analysis may be combined into one analysis depending on when the ancestral strain arm of the study and the updated Novavax vaccine arm are executed.

### 9.5 Final Analysis

The final analysis will be performed when safety data throughout the study (from Day 1 through EOS) are available.

## 10 Ethical Considerations

### 10.1 Good Clinical Practice

The investigator agrees that the study will be conducted according to the principles of ICH E6(R2). The investigator will conduct all aspects of this study in accordance with all national, state, and local laws or regulations. The study will be conducted in compliance with the protocol, current GCP guidelines – adopting the principles of the Declaration of Helsinki – and all applicable regulatory requirements.

Prior to study initiation, the protocol and the informed consent documents will be reviewed and approved by the sponsor (or designee) and an appropriate ethics committee. Any amendment to the protocol or consent materials must also be approved by the study sponsor (or designee) and IRB and must be submitted/notified to the regulatory authority, as required, before they are implemented.

### 10.2 Ethics Review

Prior to the start of the study, the investigator is responsible for ensuring that the protocol and consent form have been reviewed and approved by a relevant IRB. The IRB shall be appropriately constituted and perform its functions in accordance with ICH GCP and local requirements as applicable.

The IRB shall approve all protocol amendments (except for logistical or administrative changes), written informed consent documents and document updates, participant recruitment procedures (eg, advertisements), written information to be provided to the participants, IB, available safety information, information about payment and compensation available to participants, the investigator's curriculum vitae and/or other evidence of qualifications and any other documents requested by the IRB and Regulatory Authority (Competent Authority) as applicable.

### 10.3 Informed Consent

The nature and purpose of the study shall be fully explained to each participant. They must be informed that participation is voluntary.

Documentation of informed consent (either written or via eConsent) must be obtained from each participant prior to any study procedures being performed. The process of obtaining informed consent must be documented in the participant's source documents. The authorized person obtaining the informed consent must also sign the ICF, and a copy of the ICF must be provided to the participant. Participants must be re-consented to the most current version of the ICF during their participation in the study.

Participants will be requested to provide the name and contact information for an emergency contact and to provide consent for future testing to support establishment of correlates of protection against SARS-CoV-2 infection and disease (see Section regarding sample retention).

The consent documents to be used for the study shall include all the elements of informed consent as outlined in accordance with ICH GCP and local requirements as applicable and be reviewed and approved by the appropriate IRB prior to use.

#### **10.4 Data Privacy**

All laboratory specimens, evaluation forms, reports, and other records will be identified in a manner designed to maintain participant confidentiality. All records will be kept in a secure storage area with limited access. Clinical information will not be released without the written permission of the participant, except as necessary for monitoring and auditing by the sponsor, its designee, relevant regulatory authority(ies), or the IRB.

The investigator and all employees and co-workers involved with this study may not disclose or use for any purpose other than performance of the study, any data, record, or other unpublished, confidential information disclosed to those individuals for the purpose of the study. Prior written agreement from the sponsor or its designee must be obtained for the disclosure of any said confidential information to other parties.

## 11 Oversight

### 11.1 Quality Control and Assurance

The Sponsor/designee shall implement and maintain quality control and quality assurance procedures with written standard operating procedures (SOPs) to ensure that the study is conducted and data are generated, documented, and reported in compliance with the protocol, ICH GCP, and applicable regulatory requirements.

This study shall be conducted in accordance with the provisions of the Declaration of Helsinki (October 2013) and ICH GCP (CPMP/ICH/135/95 and updates).

The investigator will be responsible for the following:

- Providing written summaries of the status of the study to the IRB annually or more frequently in accordance with the requirements, policies, and procedures established by the IRB.
- Notifying the IRB of SAEs or other significant safety findings as required by IRB procedures.

The investigator may not deviate from the protocol without a formal protocol amendment having been established and approved by an IRB, except when necessary to eliminate immediate hazards to the participant or when the change(s) involve(s) only logistical or administrative aspects of the study. Any deviations may result in the participant having to be withdrawn from the study and render that participant non-evaluable.

The identification and reporting of serious breaches of ICH GCP or the protocol to the Regulatory Authorities and Ethics Committees will be conducted according to local SOPs and regulations.

#### 11.1.1 Monitoring

The Syneos Health clinical monitor, as a representative of the sponsor, is obligated to follow the study closely. In doing so, the monitor will visit the investigator and study site at periodic intervals in addition to maintaining necessary telephone and email contact. The monitor will maintain current personal knowledge of the study through observation, review of study records and source documentation, and discussion of the conduct of the study with the investigator and personnel.

All aspects of the study will be carefully monitored by the sponsor or its designee for compliance with applicable government regulation with respect to current ICH E6(R2) guidelines and standard operating procedures.

#### 11.1.2 Audits

The investigator and institution involved in the study will permit study-related monitoring, audits, IRB review, and regulatory inspections by providing direct access to all study records. In the event of an audit, the investigator agrees to allow the sponsor, their representatives, or the regulatory authority access to all study records.

The investigator should promptly notify the sponsor of any audits scheduled by any regulatory authorities and promptly forward copies of any audit reports received to the sponsor.

### **11.1.3 Protocol Deviations**

The investigator or designee must document and explain in the participant's source documentation any deviation from the approved protocol. The investigator may implement a deviation from, or a change to, the protocol to eliminate an immediate hazard to study participants without prior IRB approval. As soon as possible after such an occurrence, the implemented deviation or change, the reasons for it, and any proposed protocol amendments should be submitted to the IRB for review and approval, to the sponsor for agreement, and to the regulatory authorities, if required.

A protocol deviation is any change, divergence, or departure from the study design or procedures defined in the protocol. An important deviation (sometimes referred to as a major or significant deviation) is a subset of protocol deviations that leads to a participant being discontinued from the study or significantly affects the participant's rights, safety, or well-being and/or the completeness, accuracy, and reliability of the study data. An important deviation can include nonadherence to inclusion or exclusion criteria or nonadherence to regulatory authority including ICH E6(R2) guidelines.

Protocol deviations will be documented by the clinical monitor throughout the course of monitoring visits. The investigator will be notified in writing by the monitor of deviations. The IRB should be notified of all protocol deviations, as appropriate, in a timely manner.

Review and categorization of protocol deviations will occur prospectively during the study prior to database lock(s).

### **11.1.4 Records**

#### **11.1.4.1 Data Capture and Management**

All required study data will be entered by study site personnel in the eCRF or by study participants in the paper diary created for the study. Data required according to this protocol will be recorded by study site personnel via data entry into the internet-based EDC software system or by study participant via the paper diary. The investigator shall ensure that all data from participant visits are promptly entered into the eCRFs in accordance with the specific instructions given. The investigator must sign each eCRF to verify the integrity of the data recorded. All internal Syneos Health and external study site personnel seeking access to the eCRF are supported by a Service Desk (if applicable). At the end of the study all data captured electronically will be provided to the investigator on CD ROM for archiving at the study site.

The Sponsor or designee is responsible for the data management of this study including quality checking of the data.

#### **11.1.4.2 Source Documentation**

The investigator must maintain source documents, such as laboratory reports, consultation reports, reactogenicity diaries and complete medical history and physical examination reports. All information in the CRF must be traceable to the participant's source documents.

The investigator/institution shall provide direct access to source data/documents for study related monitoring, audits, IRB review, and regulatory inspection.

#### 11.1.4.3 Records Retention

The investigator/institution should maintain the study documents as specified in the ICH guidelines on GCP and as required by the applicable regulatory requirements. The investigator/institution should take measures to prevent accidental or premature destruction of these documents.

It is the Sponsor's responsibility to inform the investigator/institution as to when these documents no longer need to be retained.

### 11.2 Study Termination or Study Site Closure

Although the sponsor has every intention of completing the study, they reserve the right to discontinue it at any time for clinical or administrative reasons.

The end of the study is defined as the date on which the last participant completes the last study visit (including the EOS visit and any additional long-term follow-up). Any additional long-term follow-up that is required for monitoring of the resolution of an AE or finding may be appended to the clinical study report.

## **12 Publication Policy**

The Sponsor shall retain the ownership of all data. When the study is complete the Sponsor shall arrange the analysis and tabulation of data. A clinical study report shall then be prepared, which may be used for publication, presentation at scientific meetings or submission to regulatory authorities.

The Sponsor will generally support publication of multicenter studies only in their entirety and not as individual study site data. In this case, a coordinating investigator will be designated by mutual agreement. Authorship will be determined by mutual agreement and in line with the International Committee of Medical Journal Editors authorship agreements. Authors will be provided reasonable access to all study data, statistical tables, figures, and relevant reports and will have the opportunity to review complete study results. All proposed publications based on this study must be participant to the Sponsor's approval requirements.

The Sponsor assures that the key design elements of this protocol will be posted in a publicly accessible database such as clinicaltrials.gov. In addition, upon study completion and finalization of the study report, the results of this trial will be submitted for publication and/or posted in a publicly accessible database of clinical trial results.

## **13    Financing and Insurance**

The investigator is required to provide financial disclosure information to allow the sponsor to submit the complete and accurate certification or disclosure statements required under US Title 21 CFR Part 54 and local regulations. In addition, the investigator must provide to the sponsor a commitment to promptly update this information if any relevant changes occur during the course of the investigation and for 1 year following the completion of the study.

Neither the sponsor nor Syneos Health nor the study site is financially responsible for further testing or treatment of any medical condition that may be detected during the screening process. In addition, in the absence of specific arrangements, neither the sponsor nor Syneos Health nor the study site is financially responsible for further treatment of the disease under study.

## Appendix 1      PROTOCOL CHANGE HISTORY

### Protocol Version 2.1, 26 March 2025 (revised from Version 2.0, 23 February 2023)

The following is a summary of changes made to the protocol.

Location of Change	Change/Modification in Version 2.1, 26 March 2025
Title Page	Administrative Change – Added the NCT to Clinical Trial Registry Identifiers

### Protocol Version 2.0, 23 February 2023 (revised from Version 1.0, February 10, 2023)

The following is a summary of changes made to the protocol.

Location of Change	Change/Modification in Version 2.0, 23 February 2023
Schedule of Events	Superscripted “1” on the Screening Day to correct error
Schedule of Events and Section 7.3	Changed “caused” to “may have caused” to description of concomitant medications to be recorded for consistency.
Figure 1	Removed “phone call” from flow diagram (Figure 1).
Schedule of Events footnote and throughout the document	Changed “Memory Aid” to diary for greater accuracy.
Table 7	Updated to another version

## Appendix 2 LISTINGS OF ADVERSE EVENTS OF SPECIAL INTEREST

Because it has been hypothesized that immunizations with or without adjuvant may be associated with autoimmunity, regulatory authorities have requested that Novavax instruct investigators to be especially vigilant regarding the PIMMC listed below (Table 6). Note that this regulatory request is not specific to Novavax's SARS-CoV-2 rS or Matrix-M adjuvant; and there is no current evidence to suggest that the study vaccines in this protocol are, or are not, associated with these illnesses. The list is not intended to be exhaustive, nor does it exclude the possibility that other diagnoses may be AESI.

Table 6 Potential Immune-Mediated Medical Conditions	
Categories	Diagnoses (as MedDRA Preferred Terms)
Neuroinflammatory Disorders:	Acute disseminated encephalomyelitis (including site-specific variants: eg, non-infectious encephalitis, encephalomyelitis, myelitis, myeloradiculomyelitis), cranial nerve disorders including paralyses/paresis (eg, Bell's palsy), generalized convulsion, Guillain-Barre syndrome (including Miller Fisher syndrome and other variants), immune-mediated peripheral neuropathies and plexopathies (including chronic inflammatory demyelinating polyneuropathy, multifocal motor neuropathy and polyneuropathies associated with monoclonal gammopathy), myasthenia gravis, multiple sclerosis, narcolepsy, optic neuritis, transverse myelitis, uveitis.
Musculoskeletal and Connective Tissue Disorders:	Antisynthetase syndrome, dermatomyositis, juvenile chronic arthritis (including Still's disease), mixed connective tissue disorder, polymyalgia rheumatic, polymyositis, psoriatic arthropathy, relapsing polychondritis, rheumatoid arthritis, scleroderma (including diffuse systemic form and CREST syndrome), spondyloarthritis (including ankylosing spondylitis, reactive arthritis [Reiter's Syndrome] and undifferentiated spondyloarthritis), systemic lupus erythematosus, systemic sclerosis, Sjogren's syndrome.
Vasculitis	Large vessels vasculitis (including giant cell arteritis such as Takayasu's arteritis and temporal arteritis), medium sized and/or small vessels vasculitis (including polyarteritis nodosa, Kawasaki's disease, microscopic polyangiitis, Wegener's granulomatosis, Churg-Strauss syndrome [allergic granulomatous angiitis], Buerger's disease [thromboangiitis obliterans], necrotizing vasculitis and ANCA-positive vasculitis [type unspecified], Henoch-Schonlein purpura, Behcet's syndrome, leukocytoclastic vasculitis).
Gastrointestinal Disorders:	Crohn's disease, celiac disease, ulcerative colitis, ulcerative proctitis.
Hepatic Disorders:	Autoimmune hepatitis, autoimmune cholangitis, primary sclerosing cholangitis, primary biliary cirrhosis.
Renal Disorders:	Autoimmune glomerulonephritis (including IgA nephropathy, glomerulonephritis rapidly progressive, membranous glomerulonephritis, membranoproliferative glomerulonephritis, and mesangioproliferative glomerulonephritis).
Cardiac Disorders:	Autoimmune myocarditis/cardiomyopathy. Myocarditis and/or pericarditis
Skin Disorders	Alopecia areata, psoriasis, vitiligo, Raynaud's phenomenon, erythema nodosum, autoimmune bullous skin diseases (including pemphigus),

Table 6 Potential Immune-Mediated Medical Conditions	
Categories	Diagnoses (as MedDRA Preferred Terms)
	pemphigoid and dermatitis herpetiformis), cutaneous lupus erythematosus, morphea, lichen planus, Stevens-Johnson syndrome, Sweet's syndrome.
Hematologic Disorders:	Autoimmune hemolytic anemia, autoimmune thrombocytopenia, antiphospholipid syndrome, thrombocytopenia.
Metabolic Disorders:	Autoimmune thyroiditis, Grave's or Basedow's disease, new onset Hashimoto thyroiditis a , diabetes mellitus type 1, Addison's disease.
Other Disorders:	Goodpasture syndrome, idiopathic pulmonary fibrosis, pernicious anemia, sarcoidosis.

Abbreviations: ANCA = anti-neutrophil cytoplasmic antibody; IgA = immunoglobulin A; MedDRA = Medical Dictionary for Regulatory Activities.  
[DaSilva 2013](#)

Complications specific to COVID-19 are listed below ([Table 7](#)). The list is not intended to be exhaustive, nor does it exclude the possibility that other diagnoses may be AESI.

**Table 7 Adverse Events Representing Complications Specific to COVID-19**

Categories	Diagnoses (as MedDRA System Organ Class/Preferred Term)
Respiratory/Infectious Disorders:	ARDS, pneumonitis, septic shock-like syndrome.
Cardiac Disorders:	Acute cardiac injury, arrhythmia.
Coagulopathy	Deep vein thrombosis, myocardial infarction, stroke.
Renal Disorders:	Acute kidney injury.
Hematologic Disorder	Thrombocytopenia, septic shock-like syndrome.
Inflammatory Disorders:	Cytokine Release Syndrome related to COVID-19 infection  , multisystem inflammatory syndrome in children (MIS-C).
Neurologic Disorders:	Generalized convulsions

Abbreviations: ARDS = acute respiratory distress syndrome; COVID-19 = coronavirus disease 2019; DAIDS = Division of AIDS; MedDRA = Medical Dictionary for Regulatory Activities.

 COVID-19 manifestations associated with more severe presentation and decompensation with consideration of enhanced disease potential. The current listing is based on Coalition for Epidemic Preparedness Innovations /Brighton Collaboration Consensus Meeting (12/13 March 2020) and expected to evolve as evidence accumulates ([Lambert 2020](#)).

 Cytokine release syndrome related to COVID-19 infection is a disorder characterized by nausea, headache, tachycardia, hypotension, rash, and/or shortness of breath ([DAIDS 2017](#)).

**APPENDIX 3 TOXICITY GRADING SCALE FOR CLINICAL ABNORMALITIES,  
(LOCAL AND GENERAL SYSTEMIC REACTOGENICITY,  
CLINICAL LABORATORY, AND VITAL SIGNS)**

**Table 8 FDA Toxicity Grading Scale for Local and General Systemic Reactogenicity**

Local Reaction to Injectable Product				
Clinical Abnormality	Mild (Grade 1)	Moderate (Grade 2)	Severe (Grade 3)	Potentially Life Threatening (Grade 4)
Pain	Does not interfere with activity	Repeated use of non-prescription pain reliever > 24 hours or interferes with activity	Any use of narcotic pain reliever or prevents daily activity	ER visit or hospitalization
Tenderness	Mild discomfort to touch	Discomfort with movement	Significant discomfort at rest	ER visit or hospitalization
Erythema/redness a	2.5 – 5 cm	5.1 – 10 cm	> 10 cm	For all participants: Necrosis or exfoliative dermatitis
Induration/swelling b	2.5 – 5 cm and does not interfere with activity	5.1 – 10 cm or interferes with activity	> 10 cm or prevents daily activity	For all participants: Necrosis
Systemic (General)				
	Mild (Grade 1)	Moderate (Grade 2)	Severe (Grade 3)	Potentially Life Threatening (Grade 4)
Fever c (°C) c (°F)	38.0 – 38.4 100.4 – 101.1	38.5 – 38.9 101.2 – 102.0	39.0 – 40 102.1 – 104	> 40 > 104
Nausea/vomiting	No interference with activity or 1 – 2 episodes/24 hours	Some interference with activity or > 2 episodes/24 hours	Prevents daily activity, or requires outpatient IV hydration	Requires ER visit or hospitalization for hypotensive shock
Headache	No interference with activity	Repeated use of non-narcotic pain reliever > 24 hours or interferes with activity	Significant; any use of narcotic pain reliever or prevents daily activity	ER visit or hospitalization
Fatigue/Malaise	No interference with activity	Some interference with activity	Significant, prevents daily activity	ER visit or hospitalization
Myalgia	No interference with activity	Some interference with activity	Significant, prevents daily activity	ER visit or hospitalization
Arthralgia	No interference with activity	Some interference with activity	Significant, prevents daily activity	ER visit or hospitalization

Abbreviations: DHHS = Department of Health and Human Services; ER = emergency room; FDA = United States Food and Drug Administration.

a In addition to grading the measured local reaction at the greatest single diameter, the measurement should be recorded as a continuous variable.

b Induration/swelling should be evaluated and graded using the functional scale as well as the actual measurement.

c Oral temperature; no recent hot or cold beverages.

Source: [DHHS 2007].

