#### 8.1.4.4 Reactogenicity Symptoms

On the day of vaccination, participants will remain in clinic (or under observation) for at least 15 minutes to be observed for any immediate reaction. Injection site specific local and general systemic reactogenicity reactions including start and stop dates will be recorded following vaccination. Any immediate reaction will be recorded as an AE on day of vaccination.

Participants will utilize their diary to record reactogenicity for the 7 days following vaccination. All participants will record reactogenicity starting on the same day of the vaccination and for a total of 7 days. Should any reactogenicity event extend beyond 7 days after vaccination (toxicity Grade  $\geq 1$ ), then it will be recorded as an AE with a start date that matches Day 8 of the reactogenicity event and followed to resolution per FDA guidelines for AE capture. The toxicity grading scale implemented in the diary is included in [Appendix 3](#).

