7.3.1 Solicited Adverse Events

Solicited AEs for this study are pre-specified in Section 8 and Appendix 2 of the Study 312 Protocol, including both injection site reactions (ie, pain, tenderness, redness, and swelling) and systemic events (ie, fatigue, headache, myalgia, arthralgia, oral temperature [for assessment of fever], vomiting) that are reported within seven days following the Day 1 vaccination. These events are considered related to the test article and are collected using a severity rating of 0 (Normal), or 1, 2, or 3 (mild, moderate or severe, respectively), using the maximal severity observed for the specific symptom post-vaccination. Notable exceptions include oral temperature and events of injection site redness and swelling, which is collected as a continuous variable and that uses the grade ranges established in TGS (Table 10 in Appendix 3). Oral temperature (fever)

will be summarized by severity according to regulatory guidance, eg, Grade 0 (Normal) < 38.0°C, Grade 1 (Mild) = 38.0 – 38.4°C, Grade 2 (Moderate) = 38.5 – 38.9°C, Grade 3 (Severe) > 39.0 – 40 °C, Grade 4 (Potential Life Threatening) > 40. Redness/Swelling will be summarized by severity according to regulatory guidance, eg, Grade 0 (Normal) < 2.5 cm, Grade 1 (Mild) = 2.5 – 5 cm, Grade 2 (Moderate) = 5.1 – 10 cm, Grade 3 (Severe) > 10 cm. Extracts of solicited AEs of redness and swelling will be reviewed by the NVX clinical team and a final memo documenting the outcomes of the adjudication will be prepared by the NVX clinical team prior to database freeze (Day 29 primary analysis) or database lock (Final analysis). Any Grade 4 (Potential Life Threatening) solicited events will be provided to NVX Biostatistician team for analysis.

The number and percentage (with two-sided exact 95% CIs using the Clopper-Pearson method) of participants reporting solicited injection site and systemic AEs within the post-vaccination window (Days 1 – 7) by the verbatim terms, by severity (mild, moderate, severe, potentially life threatening) using the maximal severity observed for the specific symptom post-vaccination, or by day after vaccination and severity will be summarized for the study vaccine group. The number of participants with a solicited AE continuing beyond Day 7 will also be reported.

The duration of solicited local and systemic AEs within the 7 days after vaccination and beyond Day 7 will be summarized by the study vaccine group using several methods described below.

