Coagulopathy	Deep vein thrombosis, myocardial infarction, stroke.
Renal Disorders:	Acute kidney injury.
Hematologic Disorder	Thrombocytopenia, septic shock-like syndrome.
Inflammatory Disorders:	Cytokine Release Syndrome related to COVID-19 infection ² , multisystem inflammatory syndrome in children (MIS-C).
Neurologic Disorders:	Generalized convulsions.

Abbreviations: ARDS = acute respiratory distress syndrome; COVID-19 = coronavirus disease 2019; DAIDS = Division of AIDS; MedDRA = Medical Dictionary for Regulatory Activities.

¹ COVID-19 manifestations associated with more severe presentation and decompensation with consideration of enhanced disease potential. The current listing is based on Coalition for Epidemic Preparedness Innovations /Brighton Collaboration Consensus Meeting (12/13 March 2020) and expected to evolve as evidence accumulates ([Lambert 2020](#)).

² Cytokine release syndrome related to COVID-19 infection is a disorder characterized by nausea, headache, tachycardia, hypotension, rash, and/or shortness of breath ([DAIDS 2017](#)).

13.3 Appendix 3: Toxicity Grading Scale for Clinical Abnormalities, (local and general systemic reactogenicity, clinical laboratory, and vital signs)

Table 10: Modified FDA Toxicity Grading Scale for Clinical Abnormalities (Local and General Systemic Reactogenicity)

Local Reaction to Injectable Product				
	Mild (Grade 1)	Moderate (Grade 2)	Severe (Grade 3)	Potentially Life Threatening (Grade 4)
Pain	Does not interfere with activity	Repeated use of non-prescription pain reliever > 24 hours or interferes with activity	Significant; any use of prescription pain reliever or prevents daily activity	Requires ER visit or hospitalization
Tenderness	Mild discomfort to touch	Discomfort with movement	Significant discomfort at rest	Requires ER visit or hospitalization
Erythema/redness ^a	2.5 – 5 cm	5.1 – 10 cm	> 10 cm	Necrosis or exfoliative dermatitis ^b
Induration/swelling ^a	2.5 – 5 cm	5.1 – 10 cm	> 10 cm	Necrosis ^b
Systemic (General)				
	Mild (Grade 1)	Moderate (Grade 2)	Severe (Grade 3)	Potentially Life Threatening (Grade 4)
Fever ^c (°C) (°F)	38.0 – 38.4 100.4 – 101.1	38.5 – 38.9 101.2 – 102.0	39.0 – 40 102.1 – 104	> 40 > 104
Nausea/vomiting	Does not interfere with activity or 1 – 2 episodes/24 hours	Some interference with activity or > 2 episodes/24 hours	Prevents daily activity, or requires IV hydration outside of hospital	Requires ER visit or hospitalization

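### Protocol Table 8 grades injection-site swelling by diameter or functional impact, but the SAP derives the grade from diameter alone, so swelling severity can be understated against the protocol scale

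*Protocol*

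**What the plan says.** **Protocol.** Section 8 sends the grading of solicited events to Appendix 3. Section 8.1.4.4 ties the same appendix to the instrument: "The toxicity grading scale implemented in the diary is included in" Appendix 3. In Table 8 of that appendix, the swelling row reads:

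- Grade 1: "2.5 – 5 cm and does not interfere with activity"
- Grade 2: "5.1 – 10 cm or interferes with activity"
- Grade 3: "> 10 cm or prevents daily activity"

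Footnote b to the row adds "Induration/swelling should be evaluated and graded using the functional scale as well as the actual measurement".

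**SAP.** Section 7.3.1 says that most solicited events are collected as a rating from 0 to 3. Oral temperature, redness and swelling are the exceptions: they are collected as measurements and mapped to grades. For redness and swelling the mapping is "Grade 1 (Mild) = 2.5 – 5 cm, Grade 2 (Moderate) = 5.1 – 10 cm, Grade 3 (Severe) > 10 cm", with anything under 2.5 cm as Grade 0. The swelling row of SAP Table 10 (Appendix 3) also gives centimetres only for Grades 1 to 3.

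**Pain and headache.** For Grade 3 pain the protocol has "Any use of narcotic pain reliever or prevents daily activity" and SAP Table 10 has "Significant; any use of prescription pain reliever or prevents daily activity". Grade 3 headache differs in the same way. For Grade 2 headache the protocol refers to non-narcotic pain relievers and the SAP to non-prescription ones. The Grade 2 pain wording is the same in both.

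**The concern.** Severity of solicited reactions in the first 7 days is part of a secondary safety endpoint in both documents. SAP section 7.3.1 tabulates it by maximal grade with exact 95% confidence intervals. If the protocol defines a swelling grade by size or function and the SAP programs it from size alone, the published swelling table will not be on the scale that the protocol says participants used.

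The difference has a direction. Dropping a criterion that can only raise a grade can only lower the result. It can also take some participants out of the table altogether, because a small swelling that interferes with activity becomes Grade 0.

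**Working it through.** The plan states no figure to reproduce here, so the check compares the two rules cell by cell.

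**Inputs**

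- Size bands: under 2.5, 2.5–5, 5.1–10 and over 10 cm (the same cut-points in Protocol Table 8 and SAP section 7.3.1).
- Functional states: none, interferes with activity, prevents daily activity (Protocol Table 8).

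**Rules**

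- Size grade: 0, 1, 2, 3 for the four bands in order.
- Functional grade, from the Table 8 cells: none = 0, interferes = 2, prevents = 3.
- Protocol grade = the larger of size grade and functional grade. This follows from the word *or* in the Grade 2 and Grade 3 cells and from the no-interference condition in Grade 1. Where two cells are met, the higher one is taken.
- SAP grade = size grade.

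**Result (protocol / SAP)**

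| Size | No impact | Interferes | Prevents daily activity |
|---|---|---|---|
| < 2.5 cm | 0 / 0 | **2 / 0** | **3 / 0** |
| 2.5–5 cm | 1 / 1 | **2 / 1** | **3 / 1** |
| 5.1–10 cm | 2 / 2 | 2 / 2 | **3 / 2** |
| > 10 cm | 3 / 3 | 3 / 3 | 3 / 3 |

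Five of the 4 × 3 = 12 combinations differ, and the SAP grade is lower in every one. The two in the top row fall to Grade 0, so any-grade incidence can change as well as the Grade 2–3 counts. If Table 8 were instead read so that a swelling under 2.5 cm is never graded, 5 − 2 = 3 combinations would still differ, and any-grade incidence would not change.

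These are counts of possible combinations. They say nothing about how many participants fall in each, and the documents give no such frequency.

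**Scale of effect (illustration only)**

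Each vaccine group is to have 100–150 participants (Protocol section 5.1). One reclassified participant moves a rate by 1/150 = 0.7 to 1/100 = 1.0 percentage points. The exact (Clopper-Pearson) limits are the 0.025 quantile of Beta(k, n − k + 1), or 0 when k = 0, and the 0.975 quantile of Beta(k + 1, n − k). Suppose, as an assumption, that three participants are Grade 3 on the protocol scale and none is on the SAP scale:

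| n | SAP scale, k = 0 | Protocol scale, k = 3 |
|---|---|---|
| 100 | 0% (0 to 3.6%) | 3.0% (0.6 to 8.5%) |
| 150 | 0% (0 to 2.4%) | 2.0% (0.4 to 5.7%) |

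**Pain and headache**

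No such mapping can be made. SAP section 7.3.1 does not list pain or headache among the measurements that it maps to grades, so the grade analysed is the rating collected. The narcotic or prescription wording can act only through what the diary told the participant.

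**The case against.** **The SAP calls its table a modified scale and is entitled to define the analysis.** The label shows that the table is a variant. It does not say what was changed or that Protocol Table 8 no longer applies. The SAP change history for section 7.3.1 mentions a clarification of grading with emphasis on Grade 4 redness and swelling, and says nothing about a functional criterion. Protocol Version 2.1 (26 March 2025) is later than SAP Version 4.0 (22 August 2023) and still carries Table 8.

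**The diary is not available, and the SAP also describes it.** SAP Table 10 has its own notes on what participants report and which grades are derived. This stands: the diary may follow either table. It limits what can be said about actual counts, but one of the two documents then misdescribes the scale.

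**The sponsor's clinical team reviews redness and swelling before freeze or lock and writes a memo.** This is a real control on the affected symptom. The SAP does not say which scale the review applies at Grades 1 to 3, so it does not settle the conflict.

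**The impact is small.** This also stands. All safety analyses are descriptive, no test or decision rule depends on them, and only swelling is affected through the SAP derivation.

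**Stronger readings that the documents do not support.** A reader might infer that pain and headache counts also change, with the SAP grading them higher. That does not follow, because the SAP does not re-derive those ratings from analgesic class. A reader might also take footnote b to state a worse-of rule. It only requires both scales to be used; the rule comes from the *or* in the table cells.

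**Conclusion.** The conflict on swelling is real and should be resolved. Whenever functional impact exceeds the size band, the SAP grade is below the protocol grade: 5 of 12 combinations, by one to three grades. Any-grade and Grade 2–3 swelling rates can therefore be understated relative to the protocol scale. The conclusion rests on reading the Table 8 cells literally and on taking the highest cell met. The size of any understatement is unknown and may be nil if few swellings affect activity. It is confined to descriptive summaries of a secondary safety endpoint; the primary immunogenicity analysis is untouched.

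The pain and headache difference is a wording mismatch to check against the diary. It is not a demonstrated effect on counts.

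**What to change.** Before the Day 29 freeze, compare Protocol Table 8 and SAP section 7.3.1 with Table 10 against the scale printed in the diary, and bring both documents into line with it.

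- If the diary captured functional impact for swelling, derive the grade from size or function, as the *or* in the Table 8 cells requires, and amend SAP section 7.3.1 and Table 10.
- If it did not, the functional criterion cannot be recovered. State in the SAP and the clinical study report that swelling was graded by size only and departs from the protocol scale.
- Check the pain and headache text in the diary and align whichever table differs from it.
- If the freeze has passed, report in the clinical study report which scale was used and any departure from the protocol scale or the SAP. SAP section 1.3 already requires deviations from the SAP to be described and justified there.

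The cost is a table edit and, in the first case, a change to one derivation. Reported swelling severity may rise slightly. Whether existing data suffice depends on what the diary recorded.
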